9.5.5 Pharmacokinetics

Online pharmacokinetics

All patients who have a body weight of 40 kg or less at study entry in the Core or Extension Phase will have samples taken at Month 1 of the Core Phase and/or Extension Phase, respectively for on-line pharmacokinetic analysis. Only patients in the fingolimod group in

the Core Phase or patients switched from interferon b-1a to fingolimod in the Extension Phase will have their samples analyzed.

The Month 1 Core Phase and/or Extension Phase pharmacokinetic samples from all patients treated with fingolimod weighing 40 kg or less will be evaluated for dose optimization (need for increase to 0.5 mg). These samples will be analyzed within one month (online analysis) to ensure the systemic exposure is adequate. The results should be available for the Month 2 Core Phase and/or Extension Phase visit where the dose adjustment, if needed, would take place.

The pre-dose concentration at Month 1 Core Phase and/or Extension Phase and the approximately 6-hour post-dose concentration (good marker of fingolimod-P peak concentration), will be averaged to provide a surrogate for the average concentration (C_{av}).

If in a patient weighing 40 kg or less, who has been receiving 0.25 mg/day fingolimod, C_{av} is greater than 65% of target concentration of 1.35 ng/mL, i.e. 0.9 ng/mL, the patient will continue on the 0.25 mg dose. If in such a patient C_{av} is smaller than 65% of the target concentration i.e. smaller than 0.9 ng/mL, the dose will be increased to 0.5 mg/day.

Population pharmacokinetic analysis

Core Phase:

A population pharmacokinetic analysis will be used to characterize the key pharmacokinetic parameters in this patient population. Additionally, this analysis will also determine whether there are population covariates that affect the pharmacokinetics of fingolimod-P when administered to this patient population.

The effect of covariates on pharmacokinetic parameters will be explored. Covariates examined will include age, weight, gender, and ethnicity, as well as comedications such as oral ketoconazole which has been shown to interact with fingolimod or fingolimod-P in adults (increase in fingolimod and fingolimod-P plasma concentrations). The choice of covariates to be included in the model will be guided by exploratory plots of random effects (inter-individual variability parameters) against covariates. Those that are judged to show evidence of a relationship with the random effects will be tested for entry into the model, using the likelihood-ratio test with $p < 0.05$. The final covariate model will be derived using a rigorous and acceptable model building procedure.

Population pharmacokinetic/pharmacodynamic analysis

Core Phase:

Population PK/PD modeling approaches will be used to relate the individual fingolimod PK parameter estimates to key efficacy measurements (MRI-related, relapse-related). A modeling plan will be prepared before final clinical data lock providing details for the proposed PK/PD analysis.

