- 0.25 mg/day for all patients weighing 40 kg or less. This dose may be increased based on the results of the Month 1 online pharmacokinetic analysis or if the patient has a sustained bodyweight increase to above 40 kg during the study (sustained over at least 2 visits 3 months apart).

This approach is expected to provide exposures considered safe and effective based on data available in adults. The majority of the study population, aged 10 to less than 18 years, is expected to have a bodyweight of at least 30 kg. Children below 20 kg are nonexistent in this age range, children below 25 kg occur with a 5% frequency at an age of 10 years.

All patients weighing 40 kg or less at start of Core and/or Extension Phase will have blood sampling for PK analysis conducted at Month 1 Core Phase and/or Month 1 Extension Phase, respectively. For patients treated with fingolimod, the Month 1 Core Phase and/or Month 1 Extension Phase pharmacokinetic samples will be analyzed as soon as possible (online analysis) to ensure the systemic exposure is adequate (see Section 6.7, online pharmacokinetics, for details). If the systemic exposure is below 65% of the target exposure, the dose for the individual patient will be increased to 0.5 mg at the Month 2 Core Phase and/or Month 2 Extension Phase visits via the Interactive Voice Response system (IVR system). This rapid turnover of the results and fast implementation of a dose adjustment will limit the period of potential under-exposure for the fingolimod-treated patient.

At the Month 2 Core Phase and/or Month 2 of the Extension Phase visit, all patients in the ≤ 40 kg group will again undergo the first dose monitoring procedure described in Section 3.1 and in Appendix 2.

Patients weighing 40 kg or less who have an increase in body weight over 40 kg, sustained over at least two visits, 3 months apart, will again undergo the first dose monitoring procedure described in Section 3.1 and in Appendix 2.

The flexible treatment duration of up to 24 months for the Core Phase has been chosen to allow for sufficient time to adequately assess the effects on disease activity, as measured by relapses and brain MRI, and to determine the safety and tolerability profile of chronic treatment in the pediatric MS population.

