Fingolimod and fingolimod-P will be measured in whole blood using a validated LC-MS/MS with a LLOQ of 0.020 ng/mL and of 0.025 ng/mL, respectively.

7 Safety monitoring

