2 Statistical and analytical plans

The planned analysis is described in Section 9 of the protocol (or CSR Appendix 16.1.1).

Unless otherwise stated, summary tables/figures/listings will be on all subjects in the respective analysis set.

Categorical data will be presented as frequencies and percentages. For continuous data, mean, standard deviations, median, 25th and 75th percentiles (for some MRI parameters only), minimum and maximum will be presented.

The primary objective of the study is to compare fingolimod (FTY720) with interferon beta-1a and to demonstrate that FTY720 is superior to interferon beta-1a in terms of annualized relapse rate for the pediatric patients with RRMS (i.e., children/adolescent MS patients aged 10 to less than 18 years) treated for up to 24 months. The FTY720 arm includes patients receiving FTY720 0.5mg once daily (if body weight >40 kg at randomization) and a small number of patients receiving 0.25 mg FTY720 once daily (if body weight ≤40kg at randomization). The low dose may be switched to full dose if the 2-month PK data indicating insufficient serum level exposure or the patient's body weight increased to >40kg during the study.

The statistical models specified in this document may be modified by including fewer covariates in the models in case the pre-specified models do not converge after fitting to the trial data from final database lock.

3 Subjects and treatments

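### The online-PK dose-increase cut-off is given as 65% of 1.35 ng/mL and as 0.9 ng/mL; 65% of 1.35 is 0.8775, and the protocol does not say which value governs

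*Protocol*

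**What the plan says.** Protocol Section 9.5.5 (Online pharmacokinetics) averages two Month 1 concentrations, one pre-dose and one about 6 hours post-dose, into C_av. It then sets a yes/no rule for fingolimod patients weighing 40 kg or less who are on 0.25 mg.

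- **Continue branch:** the patient stays on 0.25 mg if C_av is above "65% of target concentration of 1.35 ng/mL, i.e. 0.9 ng/mL".
- **Increase branch:** C_av "smaller than 65% of the target concentration i.e. smaller than 0.9 ng/mL, the dose will be increased to 0.5 mg/day".

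Section 3.3 states the increase rule as a percentage only: "If the systemic exposure is below 65% of the target exposure, the dose for the individual patient will be increased to 0.5 mg". For details it points to Section 6.7, but Section 6.7.2 covers sampling and assay and gives no cut-off. The subsection that does is Section 9.5.5.

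The SAP (Section 2) mentions that the low dose may be switched on PK grounds, but gives no cut-off.

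**The concern.** Section 9.5.5 presents the percentage and the concentration as the same number, in both branches, and they are not equal at the precision of the inputs. The cut-off is operative. It triggers a dose change for the individual patient at Month 2 through the IVR system. Apart from a sustained rise in body weight, Section 5.1 allows no other dose adjustment. The decision is made behind the blind, since Section 5.4 lists the on-line PK analyst among the unblinded personnel, so site staff are not placed to notice if the rule is applied inconsistently. The same test is applied again in the Extension Phase to patients who switch from interferon. At stake is whether two people applying the protocol correctly would reach the same dose decision for the same C_av.

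**Working it through.** **Inputs**

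- Target concentration 1.35 ng/mL, fraction 65%, stated cut-off 0.9 ng/mL: Protocol Section 9.5.5.
- Fraction 65% with no concentration: Protocol Section 3.3.
- Assay limits, fingolimod and fingolimod-P: "LLOQ of 0.020 ng/mL and of 0.025 ng/mL, respectively" (Protocol Section 6.7.2).

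**Step 1. Reproduce the stated figure.** Cut-off = fraction × target = 0.65 × 1.35 = 0.8775 ng/mL. To one decimal this is 0.9, which matches the protocol. To two decimals it is 0.88, which does not.

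**Step 2. Could rounding of the inputs explain 0.9?** Let each input vary within its own rounding: 0.645 × 1.345 = 0.868 and 0.655 × 1.355 = 0.888. The range 0.868 to 0.888 does not reach 0.90. So 0.9 arises only by rounding the product to one decimal.

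**Step 3. Work back from 0.9.** 0.9 / 1.35 = 66.7% of target. For 0.9 to be 65%, the target would have to be 0.9 / 0.65 = 1.385 ng/mL.

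**Step 4. Size of the gap.** 0.9 − 0.8775 = 0.0225 ng/mL. Relative to the target, 0.0225 / 1.35 = 1.7%. Relative to the computed cut-off, 0.0225 / 0.8775 = 2.6%.

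**Step 5. Which C_av values are treated differently?** Strictly between 0.8775 and 0.9, the percentage form says continue and the ng/mL form says increase. The values affected depend on the precision at which C_av is compared:

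| Decimals in C_av | Values with opposite instructions |
|---|---|
| 1 | none |
| 2 | 0.88, 0.89 |
| 3 | 0.878 to 0.899 (22 values) |

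**Step 6. Ties.** Section 9.5.5 covers only values above and values below the cut-off. At one decimal the opposite-instruction problem disappears, but a C_av of 0.9 then sits exactly on the ng/mL form, where neither branch gives an instruction.

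**Step 7. How often might C_av fall in the band?** The documents give no distribution for C_av, so this is an illustration under assumptions. Take C_av as lognormal with geometric mean g and coefficient of variation CV, and s = √ln(1 + CV²). The share in the band is Φ(ln(0.9/g)/s) − Φ(ln(0.8775/g)/s). Over g from 0.7 to 1.35 ng/mL and CV from 20% to 50%, this runs from about 0.5% (g = 1.35, CV 20%) to about 5% (g = 0.9, CV 20%) of the patients tested.

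**The case against.** The best reply is that there is one cut-off, not two. Both branches join the forms as restatements of each other, and 0.9 is what 0.8775 becomes at one decimal. Section 3.3 is a rationale section that defers for details, so it need not be read as a rival rule. This stands as an account of where 0.9 came from. It does not settle how the rule is applied: the protocol does not call 0.9 rounded, does not say which form governs, and does not give the precision of C_av. The two-decimal target and the three-decimal assay limits suggest that C_av is finer than one decimal, but no section says so.

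A second reply is that the band is small against the measure. C_av is a surrogate built from two samples, and 1.7% of target may be within its imprecision. That limits the practical weight. It does not make the rule unambiguous, because a yes/no decision still needs one number.

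A third reply concerns the analyses, and it largely stands. A reader might infer that an inconsistent dose decision would distort the efficacy or safety comparison. The plan does not support that:

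- Efficacy is analysed on the full analysis set by randomised arm, and the SAP (Section 2) includes both strengths in the fingolimod arm, with "a small number of patients receiving 0.25 mg FTY720 once daily". The dose choice moves no one between groups.
- Safety is grouped by treatment, and the SAP's analysis sets specify no comparison by dose strength.
- The subgroup at or below 40 kg is only summarised (SAP Section 4.2.3).
- The PK/PD modelling uses individual PK parameter estimates.

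**Conclusion.** The protocol's cut-off is imprecise as written. Its two forms differ by 0.0225 ng/mL, and a C_av between 0.8775 and 0.9 ng/mL could be handled either way if compared at two or more decimals. A tie with the cut-off is undefined in Section 9.5.5 at any precision.

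A reader might go further and infer that some patients were given the wrong dose, or that the protocol holds two independent rules. The documents support neither. They do not show that any patient's C_av fell in the band, and the second figure is most simply explained as unstated rounding.

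The effect is confined to patients of 40 kg or less on 0.25 mg fingolimod whose Month 1 samples are evaluated, a group whose size is not given. Sample size, power, alpha and the by-arm primary and key secondary comparisons do not change. The arithmetic rests only on figures in the protocol. The consequence rests on the assumption that C_av is compared more finely than one decimal. The 0.5% to 5% range rests on an assumed lognormal distribution and should be read as an order of magnitude.

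**What to change.** 1. Reconcile Protocol Sections 3.3 and 9.5.5 to a single cut-off whose percentage and ng/mL values agree, and correct the pointer in Section 3.3 so that it leads to the section holding the cut-off.
2. State the number of decimals at which C_av is compared, and which branch applies when C_av equals the cut-off.
3. Confirm which figure the PK analyst has applied, and whether it was the same throughout.
4. List any past decisions with C_av from 0.8775 to 0.90 ng/mL and record which form each followed. To protect the blind before the Core Phase lock, this should be done by personnel already unblinded.

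Which figure is right is for the sponsor, and nothing here argues for either. The cost is a short text correction and a brief look-back in a small group. No analysis changes.

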9.6 Sample size calculation

Core Phase:

The sample size calculations are based on the primary efficacy variable, the annualized relapse rate (ARR). The sample size calculations and power considerations follow the method outlined in [Keene et al, 2007](#) with a constant dispersion parameter k and were programmed manually using the SAS software.

Different scenarios of the anticipated treatment effect between fingolimod 0.5 mg versus IFN β -1a, have been evaluated based on the available data on fingolimod and on IFN β -1a in the Phase III program in adults. In the TRANSFORMS study (FTY720D2302), a double-blind, one-year study, fingolimod 0.5 mg was directly compared to interferon beta-1a i.m. The ARR (0.21) in patients treated with fingolimod 0.5 mg was reduced by 52% compared to the ARR (0.43) in patient treated with IFN beta-1a.

The initial assumptions for this study (based on adult patient data) are as follows: Assuming a 50% relative reduction (from 0.72 to 0.36) in the relapse rate over 24 months (ARR: $\lambda_1=0.18$ for fingolimod, $\lambda_2=0.36$ for interferon beta-1a), a sample size of 95 patients per treatment group (or 190 total) would be needed for a 24-months study in order to provide 80% statistical power to detect such a reduction at a two-sided alpha level of 0.05 (with dispersion parameter of $k=0.82$). This corresponds to information $I=16.36$ ([equation 2 in Appendix 5](#)).

The study duration can be revised based on BSSR; the power for the primary statistical test will be retained at 80%.

[figure not shown]
BSSR and End of Study:

Analysis based data reviews of the aggregate relapse data will be conducted to re-estimate the amount of information (I) generated by the study based on the relapse activity (λ) of the recruited patient population and the observed dispersion parameter (κ) in the accumulated study data. All patients will be treated as one group, and the treatment code will not be revealed in the process. Such BSSR's provide an adequate means to check assumptions that were made at the planning stage of a clinical study protocol. They do not pose a scientific risk in terms of bias or type-I-error control and can be used to modify the sample size or study duration if this is indicated by the results.

Designs which provide the same amount of information also provide the same power (for a constant treatment effect, λ_1/λ_2 , and alpha). As in a BSSR ([Friede and Schmidli 2010](#)), fitting a negative binomial model to the aggregate data (i.e., the relapse data of all patients combined) provides an estimate of the overall ARR λ and the dispersion parameter κ . For an assumed rate ratio (clinically meaningful difference of 50%) of $\theta = \lambda_1/\lambda_2$, estimates can be obtained of the ARRs in the two groups, $\lambda_1 = 2*\lambda*\theta/(1+\theta)$ for fingolimod, and $\lambda_2=2*\lambda/(1+\theta)$ for interferon beta-1a. Based on the estimated values from the BSSR, the information (I) can be determined as follows ([see equation 3 Appendix 5](#)).

$$\text{Information } I_{\text{review}} = [2/(\lambda_1 T_{\text{total}}) + 2/(\lambda_2 T_{\text{total}}) + 4 \kappa T_{2\text{total}}/T_{\text{total}}^2]^{-1}$$

where λ_1 , λ_2 , and κ are the re-estimated values assuming a rate ratio=50% at the BSSR.

- **If the Information from the BSSR ensures that the targeted 80% power for the primary analysis is maintained, then the Core Phase of the study will complete.** It means that the study has collected equivalent or more information than initially planned ($\geq 80\%$ power for the primary objective of the study). All patients can roll over into the Extension Phase.
- 
- Any data collected during follow up period but after the Core Phase data base lock will be reported in the Extension Phase.

Fingolimod Extension Phase:

The sample size for the Extension Phase can only be estimated on the basis of expected drop-out rate in the Core Phase. Assuming the drop-out rate to be 15%, we can expect to have approximately 162 patients eligible for the Extension Phase.

9.7 Power for analysis of key secondary variables

Core Phase:

For a 24-month study and assuming a fingolimod rate of n/neT2 lesions over 24 months of 2.3 a sample size of 95 per treatment group (or 190 total) will provide approximately 88% statistical power to detect a relative reduction of 50% (i.e., from 4.6 to 2.3) in the fingolimod group compared to the interferon beta-1a group. This sample size calculation assumes that the number of n/neT2 lesions over 24 months follows a negative binomial distribution. A negative binomial dispersion estimate of 2.0 was assigned which is within the 95% confidence interval. Using the same assumptions as above with a dispersion estimate of 2.67 will provide approximately 79% statistical power to detect a relative reduction of 50% (i.e., from 4.6 to 2.3) in the fingolimod group. These estimates were based on the FREEDOMS study (FTY720D2301).

As illustrated by the above sample size calculations, sample size requirements for the n/ne T2 endpoint are lower than those for the primary endpoint. It is therefore assumed that the power for the key secondary endpoint can be maintained at $\geq 80\%$ even if the study duration is revised based on the results from the BSSR.

9.8 Interim analyses

Interim analyses for the Data Monitoring Committee (DMC) may be performed (see [Section 7.4](#)).

10 Ethical considerations

10.1 Regulatory and ethical compliance

This clinical study was designed and shall be implemented and reported in accordance with the ICH Harmonized Tripartite Guidelines for Good Clinical Practice, with applicable local regulations (including European Directive 2001/20/EC, US Code of Federal Regulations Title 21, and Japanese Ministry of Health, Labor, and Welfare), and with the ethical principles laid down in the Declaration of Helsinki.

10.2 Informed consent procedures

Eligible patients may only be included in the study after providing written (witnessed, where required by law or regulation), IRB/IEC-approved informed consent, or, if incapable of doing so, after such consent has been provided by a legally acceptable representative of the patient. In cases where the patient's representative gives consent, the patient should be informed about the study to the extent possible given his/her understanding. If the patient is capable of doing so, he/she should indicate assent by personally signing and dating the written informed consent document or a separate assent form. Informed consent must be obtained before conducting any study-specific procedures (i.e. all of the procedures described in the protocol). The process of obtaining informed consent should be documented in the patient source documents.

Novartis will provide to investigators in a separate document a proposed informed consent form that complies with the ICH GCP guideline and regulatory requirements and is considered appropriate for this study. Any changes to the proposed consent form suggested by the investigator must be agreed to by Novartis before submission to the IRB/IEC, and a copy of the approved version must be provided to the Novartis monitor after IRB/IEC approval.

Females 16 years or older, or in case there is a concern that a female patient of child-bearing potential is or might become sexually active, as assessed by the investigator, the patient and her parents/caregivers should be informed about the potential risks of pregnancy and the need to prevent pregnancy during the study. Please also refer to [Section 6.6](#).

Females of childbearing potential who are or might become sexually active, should also be informed that taking the study drug may involve unknown risks to the fetus if pregnancy were to occur during the study and agree that in order to participate in the study they must adhere to the contraception requirement for the duration of the study. If there is any question that the patient will not reliably comply, they should not be entered in the study.

10.3 Responsibilities of the investigator and IRB/IEC

The protocol and the proposed informed consent form must be reviewed and approved by a properly constituted Institutional Review Board/Independent Ethics Committee/Research Ethics Board (IRB/IEC) before study start. A signed and dated statement that the protocol and informed consent have been approved by the IRB/IEC must be given to Novartis before study initiation. Prior to study start, the investigator is required to sign a protocol signature page confirming his/her agreement to conduct the study in accordance with these documents and all of the instructions and procedures found in this protocol and to give access to all relevant data

and records to Novartis monitors, auditors, Novartis Clinical Quality Assurance representatives, designated agents of Novartis, IRBs/IECs/REBs, and regulatory authorities as required. If an inspection of the clinical site is requested by a regulatory authority, the investigator must inform Novartis immediately that this request has been made.

10.4 Publication of study protocol and results

Novartis assures that the key design elements of this protocol will be posted in a publicly accessible database such as clinicaltrials.gov. In addition, upon study completion and finalization of the study report the results of this trial will be either submitted for publication and/or posted in a publicly accessible database of clinical trial results.

11 Protocol adherence

Investigators ascertain they will apply due diligence to avoid protocol deviations. Under no circumstances should the investigator contact Novartis or its agents, if any, monitoring the trial to request approval of a protocol deviation, as no authorized deviations are permitted. If the investigator feels a protocol deviation would improve the conduct of the study this must be considered a protocol amendment, and unless such an amendment is agreed upon by Novartis and approved by the IRB/IEC it cannot be implemented. All significant protocol deviations will be recorded and reported in the CSR.

